7.2.1. Critical Baseline Assessments

Cardiovascular medical history/risk factors will be assessed at baseline.

7.3. Safety Evaluations

CBC will be monitored twice weekly in the first 4 weeks, followed by once weekly x 4 weeks and then every 4 wks thereafter. CBC may be monitored more frequently according to the institutional guideline.

Planned time points for all safety assessments will include physical exam, vital signs, clinical laboratory tests including chemistry, hematology, and coagulation panel, ECGs and ECOG performance status. AEs and toxicities will be assessed throughout the study and will be graded according to NCI-CTCAE v. 4.03.

Additional time points for safety assessment may be added during the course of the study based on emerging pharmacokinetic and safety data to ensure appropriate safety monitoring.

Planned time points for all safety assessments are provided in the Time and Events Table (Section [7.1](#)).

7.3.1. Physical Examinations

A complete physical examination will include assessments of the head, eyes, ears, nose, throat, skin, thyroid, neurological, lungs, cardiovascular, abdomen (liver and spleen), lymph nodes and extremities. Height and weight will also be measured and recorded.

A brief physical examination will include assessments of the skin, lungs, cardiovascular system, and abdomen (liver and spleen).

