RA-APL syndrome or respiratory compromise	About 25% of patients with APL treated with ATRA have experienced the retinoic acid-APL (RA-APL) syndrome.	Protocol provides the guideline for RA-APL syndrome management.
Leukocytosis	About 40% of patients may develop rapidly evolving leukocytosis during ATRA treatment	Subjects with an increased risk of a further rapid increase in WBC counts, i.e., WBC >30,000/uL, are excluded.
Pseudotumor cerebri/intracranial hypertension.	ATRA may cause pseudotumor cerebri/intracranial hypertension.	Concomitant administration of ATRA and agents known to cause pseudotumor cerebri/intracranial hypertension (e.g., tetracycline) will be prohibited.
Hypercholesterolemia/hypertriglyceridemia	Up to 60% of patients experienced hypercholesterolemia and/or hypertriglyceridemia with ATRA treatment.	Subjects with hypertriglyceridemia or hypercholesterolemia >300 mg/dL are excluded. Lipid panel will be checked weekly for the first 4 weeks and then q 4 weeks thereafter.
Liver function test elevation	Elevated liver function test results occur in 50% to 60% of patients during ATRA treatment.	LFT is monitored twice weekly for the first 2 weeks, weekly for the next 2 weeks and then q 4 weeks thereafter. Treatment stopping criteria based on elevation in LFT is in place and the safety management guideline is also provided.
Hypervitaminosis A	Chemically, ATRA is all-trans retinoic acid and is related to retinol (Vitamin A).	Vitamin A or multivitamins including vitamin A are prohibited.
Teratogenic effect	There is a high risk that a severely deformed infant will result if ATRA is administered during pregnancy.	Female subjects with child bearing potential will be required to use 2 reliable forms of contraception methods simultaneously during the treatment and until 30 days after the last dose of ATRA or 7 days after the last dose of GSK2879552, whichever is later. Contraception counselling will be repeated monthly throughout ATRA treatment. Serum pregnancy test will be performed at screening and end of treatment visit, and urine pregnancy test at week 4 and every 4 weeks thereafter.

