4.8.4. Safety Management for ATRA Combination

4.8.4.1. Retinoic Acid syndrome

About 25% of patients with APL treated with ATRA have experienced the retinoic acid-(RA) syndrome characterized by fever, dyspnea, acute respiratory distress, weight gain, radiographic pulmonary infiltrates, pleural and pericardial effusions, edema, and hepatic, renal, and multi-organ failure [ATRA Prescribing Information, 2004]. This syndrome has occasionally been accompanied by impaired myocardial contractility and episodic hypotension. The syndrome generally occurs during the first month of treatment, with some cases reported following the first dose of ATRA.

Retinoic Acid Syndrome should be strongly suspected if the following signs or symptoms (without any other clear or established etiology) emerge during treatment with GSK2879552:

- New or worsening progressive dyspnea or hypoxemia, with increasing demands for supplemental oxygen; respiratory distress refractory to treatment for the initially suspected cause
- Radiologic evidence of new or worsened bilateral pulmonary involvement (infiltrates or opacities) with or without presence of infection, refractory to treatment with anti-infectives (antibiotics, antivirals, antifungals)
- Radiologic evidence of new or worsened pleural or pericardial effusion that is refractory to treatment for an initially suspected cause
- New or worsened peripheral edema, with rapid weight gain (e.g., >5 kg/11 pounds over 7 days)
- Increase in serum creatinine (e.g., >2-fold from baseline)
- The following symptoms or signs may be features of retinoic acid syndrome but if isolated and not accompanied by pulmonary or renal manifestations, may not require rapid initiation of retinoic acid syndrome treatment (unless sufficiently severe and prolonged):
 - Unexplained fever $\geq 38^{\circ}\text{C}$ (100.4°F)
 - Rash of unknown origin
 - Bone pain

- Lymphadenopathy

The measures below are recommended to be taken at the earliest manifestations of suspected retinoic acid syndrome:

- Patients with severe or rapidly progressing retinoic acid syndrome should be hospitalized for continued observation
- In case of uncertainty with the diagnosis, e.g., presence of less specific symptoms of moderate severity, patients should be closely monitored, as the condition may rapidly worsen

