- Corticosteroids should be promptly initiated (e.g., 10 mg of dexamethasone every 12 hours until resolution of retinoic acid syndrome). Once resolved the corticosteroid dose can be progressively reduced over 1-2 weeks
- GSK2879552 and/or ATRA may be withheld at the physician's discretion. Due to the long half-life of GSK2879552 (about 16 hours), treatment interruption may not immediately reverse the symptoms of retinoic acid syndrome. If interrupted, GSK2879552 treatment may be reinitiated at the original or a reduced dose, once the signs and symptoms resolve and the patient's clinical condition improves
- In patients with elevated WBC counts, prompt initiation of hydroxyurea is suggested, or treated as per standard local practice (e.g., dose of 2 to 3g PO 2- or 3-times daily for WBC $>30 \times 10^9/L$)
- In cases of severe leukocytosis, use of leukapheresis may be appropriate
- For substantial fluid accumulation, initiation of furosemide may be appropriate, as per local standard practice
- Patients with pericardial effusion (a less common manifestation of retinoic acid syndrome) can require urgent cardiac intervention due to it being a life-threatening condition
- Patients with increasing serum creatinine levels should be evaluated for tumor lysis syndrome
- Patients experiencing a rapid increase in peripheral blood cells should be monitored for disseminated intravascular coagulopathy and hemorrhage
- Imaging techniques such as standard or high-resolution computerized tomography (CT) scan and chest X-ray are useful for establishing a diagnosis of retinoic acid syndrome by identifying pulmonary infiltrates or effusions; noting that a CT scan is more sensitive in detecting early radiological signs of retinoic acid syndrome-associated changes

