7. STUDY ASSESSMENTS AND PROCEDURES

A signed, written informed consent form must be obtained from the subject prior to any study-specific procedures or assessments being performed.

The timing of each assessment is listed in the Time and Events Table (Section 7.1). The timing and number of the planned study assessments may be altered during the course of the study based on newly available data (e.g. to obtain data closer to the time of peak plasma concentrations) to ensure appropriate monitoring for the following assessments: safety, PK, PD/biomarker assessments. The change in timing or addition of time points for any of the planned study assessments listed above must be approved and documented by GSK, but this will not constitute a protocol amendment. The institutional review board (IRB) or ethics committee (EC) will be informed of any safety issues that require alteration of the safety monitoring scheme.

Whenever vital signs, 12-lead ECGs and blood draws are scheduled for the same nominal time, the assessments should occur in the following order: 12-lead ECGs, vital signs, blood draws.

If the blood draw is done first, there should be at least 15 minute interval before the vital signs and 12-lead ECGs measurements are taken.

On clinic days, study drug should be taken in the clinic after all the safety procedures (including CBC) and blood sampling for PK/PD, if applicable, are completed.

Detailed procedures for obtaining each assessment are provided in the Study Procedures Manual (SPM).

Visit Window

Informed consent should be signed within 35 days prior to dosing.

Baseline disease assessment should be completed within **21 days** prior to dosing start.

ECHO/MUGA should be completed within **35 days** prior to dosing start.

Pregnancy testing should be completed **7 days** prior to dosing start and all other screening assessments should be completed within **14 days** prior to dosing start.

Visits in the first 4 weeks will be allowed ± 1 day window. Bone marrow on Day 15 can be done between Day 8 and Day 21.

Visits beyond the first 4 weeks will have ± 3 days window.

The End of Treatment visit should be completed within **14 days** from the last dose.

Time Window for PK sampling

0.25, 0.5, 1 and 1.5 hours post dose sampling: ± 5 minutes

2, 3, 4 hours post dose sampling: ± 10 minutes

6, 8, and 10 hours post dose sampling: ± 30 minutes

24 hours post dose sampling: ± 1 hour and should be done before the next dose administration.

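### In the ATRA arm, no weight or brief physical examination is scheduled between D8 and Week 4, most of the month in which retinoic acid syndrome is expected

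*Protocol*

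**What the plan says.** Protocol Section 4.8.4.1, which applies to the ATRA combination, says of retinoic acid syndrome: "The syndrome generally occurs during the first month of treatment". Among the findings that should raise strong suspicion it lists: "New or worsened peripheral edema, with rapid weight gain (e.g., >5 kg/11 pounds over 7 days". On timing of action it states: "The measures below are recommended to be taken at the earliest manifestations of suspected retinoic acid syndrome". The treatment instruction is: "Corticosteroids should be promptly initiated".

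Section 7.3.1 defines two examinations. The complete one lists extremities and includes weight; Tables 3 and 4 schedule it at screening and end of treatment only. The other is described so: "A brief physical examination will include assessments of the skin, lungs, cardiovascular system, and abdomen (liver and spleen". Weight is a separate row in both tables. Weight and the brief examination share one schedule: D1, D8, then every 4 weeks. The vital signs defined in Section 7.3.4 do not include weight. The footnote for the ATRA arm (22 in Table 3, 18 in Table 4) adds chemistry on D4 and D11 and a fasting lipid panel, but no weight and no examination.

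The risk table in Section 1.4.5.1 gives this mitigation for the syndrome: "Protocol provides the guideline for RA-APL syndrome management". For lipids it gives a calendar: "Lipid panel will be checked weekly for the first 4 weeks and then q 4 weeks thereafter".

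**The concern.** A weight gain over 7 days can be judged only from two weights about a week apart. New or worsened edema can be judged only by looking more than once. The plan names this sign, names the month in which the syndrome usually appears and asks for action at the first manifestations. It then schedules neither a weight nor a brief examination for most of that month.

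What is at stake is the timing of recognition. A patient who gains fluid between D8 and Week 4 might not report it, and nobody is required to weigh the patient. Section 4.8.4.1 associates the syndrome with respiratory distress and multi-organ failure, so a delay in starting corticosteroids could matter to that patient. The trial's statistical conclusions are not at stake: no hold rule, DLT criterion or endpoint is defined on weight.

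**Working it through.** The plan states no figure for this gap, so the check is a reading of the schedule and a day count.

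**Inputs.** Schedule: Protocol Section 7.1, Tables 3 and 4. Windows: Section 7, which says "Visits in the first 4 weeks will be allowed ± 1 day window" and allows ±3 days after that. First phase: 28 days. Assumption: the four-weekly entry for weight and examination starts at Week 4, taken as D28 or D29. The tables do not name Week 4 in these rows; a later start would only lengthen the gap.

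**What is scheduled after D1 and before Week 4 in the ATRA arm.**

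| Assessment | Days | Count |
|---|---|---|
| Chemistry, including creatinine | D4, D8, D11, D15, D22 | 5 |
| Fasting lipids | D8, D15, D22 | 3 |
| Weight | D8 | 1 |
| Brief examination | D8 | 1 |

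Office visits after D8 and before Week 4: six in Part 1 (D11, D15, D16, D18, D22, D25) and five in Part 2 (no D16). None carries a weight or a brief examination.

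**Days of the 28-day phase left unchecked after D8, nominal.**
- Week 4 = D28: D9 to D27 = 19 days; 19/28 = 68%.
- Week 4 = D29: D9 to D28 = 20 days; 20/28 = 71%.

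**With windows.** The D8 visit can fall on D7 to D9. The Week 4 visit can fall on D25 to D32, using ±3 days around D28 or D29 as the widest case.
- Shortest: checks on D9 and D25 leave D10 to D24 = 15 days; 15/28 = 54%.
- Longest inside the phase: a check on D7 and the next one after D28 leave D8 to D28 = 21 days; 21/28 = 75%.

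**Intervals between scheduled weights.** D1 to D8 is 7 days, the one interval that fits the 7-day example. The D1 weight may be omitted if screening was within 3 days, in which case this interval can stretch to 7 + 3 = 10 days. The next interval is 28 − 8 = 20 or 29 − 8 = 21 days nominally; with windows it runs from 25 − 9 = 16 to 32 − 7 = 25 days.

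**With weights added at D15 and D22.** Nominal intervals: 15 − 8 = 7, 22 − 15 = 7, and 28 − 22 = 6 or 29 − 22 = 7 days. Longest with windows: D7 to D16 = 9, D14 to D23 = 9, D21 to D32 = 11 days. Scheduled weights strictly between D8 and Week 4 rise from 0 to 2.

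**The case against.** The strongest reply is that surveillance in the gap is already dense. Patients attend five or six times. Creatinine, itself a listed ground for suspicion, is tested on D11, D15 and D22. Respiration rate and temperature are taken on D15, blood counts are twice weekly and adverse events are collected throughout. Section 4.8.4.1 asks sites to suspect the syndrome whenever its signs emerge, not only on examination days, and nothing stops a site from weighing a patient. Sections 7 and 7.3 allow safety time points to be added. Section 1.3.5 lists local edema among the events seen in more than 20% of the first 11 monotherapy subjects, so edema was being reported. All of this stands and limits the consequence. It does not schedule a weight: the option to add time points is permissive, and Section 4.1 treats adherence to the Time and Events Table as essential.

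Two supporting arguments are weaker than they look. The brief examination omits extremities, and a reader might infer that it cannot find edema. It covers skin and the cardiovascular system, either of which could reveal it. The risk table sets test calendars for lipids, liver tests and coagulation but not for this syndrome, and a reader might infer an oversight. Laboratory abnormalities need sampling, whereas this syndrome is recognised clinically and has its own detailed guidance. Both points are secondary.

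A reader might also divide the longest possible interval, 25 days, by 28 and report 89%. That interval ends on D32, so the numerator includes days outside the 28-day phase. Inside the phase the upper limit is 75%.

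Finally, the 25% syndrome rate in Section 4.8.4.1 comes from APL. FAB subtype M3 is excluded here and the protocol gives no rate for the patients studied, so no expected number of missed or late cases can be derived.

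**Conclusion.** The point holds as a gap in scheduled checks. After D8 and before Week 4, 19 to 20 of 28 days (68% to 71%) carry no scheduled weight or brief examination, and more than half the phase is uncovered under every window scenario (54% to 75%). The protocol's example of a 7-day weight gain can be assessed from scheduled weights once in the month of main risk.

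The documents do not support reading this as a blind spot, or as evidence that cases would be missed. They give no basis for saying how long recognition would be delayed. The supportable conclusion is a risk of later recognition of a fluid-retention presentation, which is one of several grounds for suspicion; the 5 kg figure is itself only an example.

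The conclusion rests on four-weekly checks starting at Week 4 and on the two tables being read correctly; they agree on these rows. It is limited to the ATRA arm, because Section 4.8.4 is written for that combination. Practical reach is small: SAP Section 2.1 says Part 2 was not started, and SAP Section 5.1 lists a single ATRA group (2 mg once daily with ATRA 45 mg/m²/day). This is a cheap improvement that should be made, not a fault that undermines the trial.

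**What to change.** In Tables 3 and 4, for the ATRA arm only, add weight and a check for peripheral edema at the existing D15 and D22 visits, with a footnote. In Section 7.3.1, add extremities (edema) to the brief examination. Leave the treatment rules in Section 4.8.4.1 as they are.

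The longest interval between scheduled weights falls from 20–21 days to 7 days nominally, and to at most 11 with windows.

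The cost is one phrase in Section 7.3.1, two cells and a footnote in each table, and a few minutes of staff time per visit. No new visit, blood draw or invasive procedure is needed. Some weight changes from hydration or transfusion will prompt further checks that prove to be false alarms.

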7.3.2. ECOG Performance Status

The performance status will be assessed using the Eastern Cooperative Oncology Group (ECOG) scale ([Appendix 4](#)) as specified in the Time and Events Table (Section [7.1](#)).

7.3.3. Montreal Cognitive Assessment

Montreal Cognitive Assessment (MOCA) was designed as a rapid screening instrument for mild cognitive dysfunction. It assesses different cognitive domains: attention and concentration, executive functions, memory, language, visuoconstructional skills, conceptual thinking, calculations, and orientation. Time to administer the MOCA is approximately 10 minutes.

The test and administration instructions are freely accessible for clinicians at www.MOCAtest.org. English version 7.1 is shown in [Appendix 8](#).

7.3.4. Vital Signs

Vital sign measurements will include systolic and diastolic blood pressure, temperature, respiration rate and heart rate. Vital signs should be measured after resting for at least 5 minutes in a semi-supine position. Vital signs will be measured more frequently if warranted by clinical condition of the subject. Refer to the SPM for details regarding measurement of vital signs.

7.3.5. Electrocardiogram

Single 12-lead electrocardiogram (ECGs) will be obtained at designated time points during the study using an ECG machine that automatically calculates the heart rate and measures PR, QRS, QT, and corrected QT (QTc) intervals. At each assessment a 12-lead ECG will be performed by qualified personnel at the site after the subject has at least a 5 minute rest and is in a semi-recumbent or supine position.

Refer to Section 4.7.2 for QTc withdrawal criteria. Additional QTc readings may be necessary.

7.3.6. Echocardiogram and/or Multi-gated Acquisition Scans

ECHOs or MUGA scans will be performed at baseline to assess cardiac ejection fraction and cardiac valve morphology for the purpose of study eligibility. Additional ECHO assessments may be performed if clinically warranted. The evaluation of the echocardiographer should include an evaluation for left ventricular ejection fraction (LVEF).

7.3.7. Laboratory Assessments

All protocol required laboratory assessments, as defined in Table 5 should be performed according to the Time and Events Table (Section 7.1).

Prior to administration of the first dose of study treatment, results of laboratory assessments should be reviewed. Any laboratory test with a value outside the normal range may be repeated (prior to the first dose) at the discretion of the investigator.

All laboratory tests with values that are significantly abnormal during participation in the study or within 30 days after the last dose of study treatment should be repeated until the values return to normal or baseline. If such values do not return to normal within a period judged reasonable by the investigator, the etiology should be identified and the sponsor notified.

Hematology, clinical chemistry, coagulation panel and additional parameters to be tested are listed in Table 5:

Table 5 List of Clinical Laboratory Tests

Hematology			
Platelet Count	RBC Indices:		Automated WBC Differential:
Red blood cell (RBC) Count	Mean corpuscular volume (MCV)		Neutrophils
White blood cell (WBC) Count (absolute)	Mean corpuscular hemoglobin (MCH)		Lymphocytes
Reticulocyte Count	Mean corpuscular hemoglobin concentration (MCHC)		Monocytes
Hemoglobin			Eosinophils
Hematocrit			Basophils
Blast count			
Clinical Chemistry			
Blood urea nitrogen (BUN)	Potassium	Aspartate aminotransferase (AST)	Total and direct bilirubin ¹
Creatinine	Chloride	Alanine aminotransferase (ALT)	Uric Acid
Glucose	Total carbon dioxide (CO ₂)	Gamma glutamyl transferase (GGT)	Albumin
Sodium	Calcium	Alkaline phosphatase	Total Protein
Phosphate	Lactate Dehydrogenase (LDH)	Thyroid Stimulating Hormone	Free T4 or Free T3
Vitamin B12			
Lipid			
Triglyceride	Cholesterol		
Other tests			
Coagulation Panel including PT, PTT, INR, fibrinogen			
Fetal hemoglobin (Hgb F)			
Other screening tests			
Follicle stimulating hormone (FSH) and estradiol (as needed in women of non-child bearing potential only)			
HIV, Hepatitis B surface antigen (HBsAg) and Hepatitis C antibody (HCV Ab) testing			

1. Direct bilirubin should be assessed only if total bilirubin is elevated beyond the upper limit of normal (ULN)

7.3.8. Pregnancy Testing and Reporting

The need for a screening pregnancy test depends on whether a female subject is of childbearing potential or non-childbearing potential.

If a female subject is of childbearing potential, she must have a serum β -HCG pregnancy test performed within 7 days prior to the first dose of study treatment(s). Subjects with positive pregnancy test result must be excluded from the study. Subjects with negative pregnancy test result must agree to use an effective contraception method as described below during the study until 7 days following the last dose of study treatment(s).

Any pregnancy that occurs during study participation must be reported using a clinical trial pregnancy form. To ensure subject safety, each pregnancy must be reported to GSK within 2 weeks of learning of its occurrence. The pregnancy must be followed up to determine outcome (including premature termination) and status of mother and child. Pregnancy complications and elective terminations for medical reasons must be reported

as an adverse event (AE) or serious adverse event (SAE). Spontaneous abortions must be reported as an SAE.

Any SAE occurring in association with a pregnancy brought to the investigator's attention after the subject has completed the study and considered by the investigator as possibly related to the study treatment(s), must be promptly reported to GSK.

In addition, the investigator must attempt to collect pregnancy information on any female partners of male study subjects who become pregnant while the subject is enrolled in the study. Pregnancy information must be reported to GSK as described above.

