10. Adequate baseline organ function defined by:

System	Laboratory Values
Hematologic	
White blood cell count (absolute)	≤30,000/uL
Coagulation assays (PT/INR and aPTT)	≤1.3 X ULN
Hepatic	
Total bilirubin	≤ 1.5 X ULN ¹
ALT and AST	≤2.5 × ULN
Renal	
Calculated creatinine clearance by Chronic Kidney Disease Epidemiology Collaboration (CKD-EPI) equation (Appendix 3) or measured from 24hr urine	≥ 40 mL/min
Cardiac	
Ejection fraction	≥ LLN by Echocardiogram (ECHO) or MUGA
Lipid (ATRA combination ONLY)	
Triglyceride (fasting)	≤ 300 mg/dL
Cholesterol (fasting)	≤ 300 mg/dL

1. Isolated bilirubin >1.5 X ULN is acceptable if bilirubin is fractionated and direct bilirubin <35% or subject has a diagnosis of Gilbert's syndrome

NOTE: Laboratory results obtained during Screening should be used to determine eligibility criteria. In situations where laboratory results are outside the permitted range, the investigator may opt to retest the subject and the subsequent within range screening result may be used to confirm eligibility.

11. Women of childbearing potential must have a negative serum pregnancy test within 7 days of first dose of study treatment and agree to use effective contraception (Section [11.1](#)), during the study and for 7 days (GSK2879552 mono therapy) or 30 days (combination with ATRA), following the last dose of study treatment.
12. Men with a female partner of childbearing potential must have either had a prior vasectomy or agree to use effective contraception (Section [11.1](#)) from the administration of the first dose of study treatment until 3 months after the last dose of study treatment to allow for clearance of any altered sperm.

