5. INVESTIGATIONAL PRODUCT(S)

The term ‘study treatment’ is used throughout the protocol to describe investigational product(s) (IP) received by the subject as per the protocol design. Study treatment may therefore refer to the individual study treatments or the combination of those study treatments.

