11. LIFESTYLE AND/OR DIETARY RESTRICTIONS

11.1. Contraception

11.1.1. Female Subjects

A female of non-childbearing potential (i.e., physiologically incapable of becoming pregnant) is defined as any female who has had a hysterectomy, bilateral oophorectomy (ovariectomy) or bilateral tubal ligation, or is post-menopausal.

A practical definition accepts menopause after 1 year without menses with an appropriate clinical profile, e.g., age appropriate, >45 years in the absence of hormone replacement therapy (HRT). In questionable cases, the subject must have a follicular stimulating hormone (FSH) value >40 mIU/mL and an estradiol value < 40pg/mL (<140 pmol/L).

A female of childbearing potential is defined as any female who does not meet the criteria of non-childbearing potential as described in the previous paragraph.

Female subjects of childbearing potential must not become pregnant during the study and so must be sexually inactive by abstinence or use contraceptive methods with a failure rate of <1%.

Female subjects of childbearing potential receiving ATRA combination treatment must use two reliable forms of contraception simultaneously during treatment and 30 days after the last dose of ATRA or 7 days after the last dose of GSK2879552, whichever is later. **Contraceptive counselling should be repeated monthly** while receiving ATRA and documented in the site source file. **Hormonal contraceptives are NOT considered acceptable form of contraception for female subjects of childbearing potential receiving ATRA combination treatment.** Intrauterine device or intrauterine system, male partner sterilization and double-barrier method as described below are acceptable forms of contraception for female subjects of childbearing potential receiving ATRA combination treatment.

Abstinence

Sexual inactivity by abstinence must be consistent with the preferred and usual lifestyle of the subject. Periodic abstinence (e.g. calendar, ovulation, symptothermal, post-ovulation methods) and withdrawal are not acceptable methods of contraception.

Complete abstinence from sexual intercourse for 7 days prior to first dose of study treatment, through the dosing period, and for at least 7 days after the last dose of study treatment.

Contraceptive Methods with a Failure Rate of $\leq 1\%$

- Oral contraceptives (either combined or progesterone only) if not contraindicated for this subject population or per local practice. – GSK2879552 monotherapy ONLY

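### For women of childbearing potential on the ATRA combination, Protocol Section 7.3.8 ends contraception at 7 days after treatment, while other passages give 30 days, with two different starting points

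*Protocol*

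**What the plan says.** Five places in the current protocol bear on how long a woman of childbearing potential must continue contraception after treatment.

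- **Section 7.3.8 (Pregnancy Testing and Reporting).** A subject with a negative test has to commit to an effective method, said to be described below, during the study and "until 7 days following the last dose of study treatment(s"). No arm is singled out.
- **Section 11.1.1, abstinence paragraph.** Complete abstinence through dosing "and for at least 7 days after the last dose of study treatment". Again no arm is singled out.
- **Inclusion criterion 11 (Section 3.2.1, repeated in the synopsis).** Contraception during the study and "for 7 days (GSK2879552 mono therapy) or 30 days (combination with ATRA), following the last dose of study treatment".
- **Section 1.4.5.1, risk table, teratogenic effect (ATRA combination only).** Two methods during treatment and "until 30 days after the last dose of ATRA or 7 days after the last dose of GSK2879552, whichever is later".
- **Section 11.1.1, ATRA paragraph.** The subject "must use two reliable forms of contraception simultaneously during treatment and 30 days after the last dose of ATRA", with the same second limb as the risk table: "30 days after the last dose of ATRA or 7 days after the last dose of GSK2879552, whichever is later".

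Section 5 fixes the scope of the common term: "Study treatment may therefore refer to the individual study treatments or the combination of those study treatments". A sentence about study treatment with no arm qualifier therefore reaches combination subjects.

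**The concern.** Section 7.3.8 is where a site would look for pregnancy-test handling, and it states a duration of its own. Read literally, it gives a combination subject a shorter period than the one she agreed to at entry, and shorter than the one the risk table offers as mitigation. The protocol describes the fetal risk of ATRA as high (Sections 1.3.6.1 and 1.4.5.1), so the length of this period is part of its stated safety case.

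The schedule would not catch a misreading. In Tables 3 and 4 the last planned pregnancy test is at the End of Treatment visit, which Section 7 places within 14 days of the last dose. That is before a 30-day period ends.

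There is a second, quieter problem. The passages that state 30 days do not all count from the same event, so aligning 7.3.8 with the 30-day passages would not by itself give a single rule.

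**Working it through.** The plan has no figure to reproduce. The check sets the passages side by side and works out when each releases a combination subject.

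**Notation.** A is the day of the last ATRA dose, G the day of the last GSK2879552 dose, and D = G − A. D is positive when ATRA stops first. The last dose of study treatment is taken as the later of A and G. This is an assumption, because the protocol does not say which drug's last dose counts.

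**Last day of required contraception under each passage**

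- Section 7.3.8: max(A, G) + 7
- Abstinence paragraph of 11.1.1: no earlier than max(A, G) + 7
- Inclusion criterion 11, combination: max(A, G) + 30
- Risk table and ATRA paragraph of 11.1.1: max(A + 30, G + 7)

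**Differences**

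- Criterion 11 minus 7.3.8: 30 − 7 = 23 days, whatever the stopping order.
- Risk table and ATRA paragraph minus 7.3.8:
  - If ATRA stops last or on the same day (D ≤ 0): (A + 30) − (A + 7) = 23 days.
  - If ATRA stops D days earlier: max(A + 30, A + D + 7) − (A + D + 7) = max(23 − D, 0) days.
- Criterion 11 minus risk table and ATRA paragraph: 0 if D ≤ 0; otherwise (A + D + 30) − max(A + 30, A + D + 7) = min(D, 23) days.

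| Stopping order | 7.3.8 ends | Risk table / 11.1.1 ATRA ends | Criterion 11 ends | 7.3.8 short of risk table / 11.1.1 | 7.3.8 short of criterion 11 | Risk table / 11.1.1 short of criterion 11 |
|---|---|---|---|---|---|---|
| Same day (D = 0) | A + 7 | A + 30 | A + 30 | 23 | 23 | 0 |
| ATRA 14 days earlier | A + 21 | A + 30 | A + 44 | 9 | 23 | 14 |
| ATRA 23 days earlier | A + 30 | A + 30 | A + 53 | 0 | 23 | 23 |

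The middle row can arise under the protocol. Section 4.8.4.2 holds ATRA for an ALT elevation while GSK2879552 continues, then holds GSK2879552 as well if there is no resolution in 14 days. A subject withdrawn on that path would have stopped ATRA about 14 days before GSK2879552. Sections 4.1 and 4.8.2 also allow ATRA to be given intermittently or held first.

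**Who is affected.** For monotherapy, 7.3.8, the abstinence paragraph and criterion 11 all say 7 days. Male subjects have their own 3-month period (criterion 12 and Section 11.1.2). The conflict is confined to women of childbearing potential in the combination arm.

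**The case against.** The best defence is that the protocol already binds the combination subject to the longer period elsewhere. She must agree to 30 days to be eligible, deviations from inclusion criteria are not allowed (Section 3.2.1), and contraceptive counselling is repeated monthly while she receives ATRA. A site would have to follow 7.3.8 alone to release her early. This makes an error less likely, but it does not make 7.3.8 agree with the other passages.

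It may also be said that 7.3.8 refers the reader onward with its words about a method described below. Those words qualify the method. The duration follows in the same sentence, with no cross-reference and no mention of arm.

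The objection has more force on abstinence. A reader might infer that this paragraph is a second direct contradiction, but the text does not go that far. At least 7 days is a minimum, and a 30-day period satisfies it. The ATRA paragraph lists acceptable forms for the combination arm and abstinence is not among them, so it is unclear whether the abstinence paragraph governs that arm at all. Against this, the general sentence earlier in 11.1.1 offers abstinence to every woman of childbearing potential, and the section marks several methods as monotherapy only without marking abstinence. What stands is an ambiguity that should be closed.

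Finally, SAP Section 2.1 records early termination, and SAP Section 5.1 lists only one combination dose group. That limits how many subjects the wording could have affected.

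**Conclusion.** The inconsistency is real and lies in the current text. For women of childbearing potential on the combination, 7.3.8 is 23 days shorter than criterion 11. It is between 0 and 23 days shorter than the risk table and the ATRA paragraph of 11.1.1: the full 23 when ATRA stops last or with GSK2879552, and nothing once ATRA has stopped 23 or more days earlier. The 30-day passages themselves differ by up to 23 days because of their starting points. These sizes rest on reading the last dose of study treatment as the later of the two drugs.

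Three stronger conclusions might be drawn, and the documents do not support them. The mismatch does not reach all subjects, since monotherapy and male subjects have consistent periods. The shortfall is not a fixed 23 days against every passage. And nothing in the documents shows that any subject was released early, or settles which period is right.

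No estimate, sample size or analysis depends on this. It deserves correction because a stated safety measure should read the same wherever a site meets it.

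**What to change.** Reconcile Section 7.3.8, the abstinence and ATRA paragraphs of 11.1.1, inclusion criterion 11 (in 3.2.1 and the synopsis) and the risk table in 1.4.5.1. Each arm should have one period and one starting point, naming the drug whose last dose counts, in identical words throughout. The sponsor should also say whether the abstinence paragraph applies to the combination arm. Editing 7.3.8 and the abstinence paragraph alone would not be enough, because criterion 11 and the ATRA paragraph would still count from different events.

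The choice of period and starting point belongs to the sponsor. The cost is a few sentences in an amendment, with no change to the trial's size, its schedule of analyses or the SAP.
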